1.0 Study Summary

1.0 Study Summa		
Study Title	Assessment of effectiveness and safety of a novel pessary for the non- surgical management of pelvic organ prolapse	
Study Design	Prospective open label feasibility study of a medical device	
Primary Objective	 To assess the effectiveness of the study pessary to support prolapse by measuring the change in the score of the Pelvic Floor Distress Inventory-20 (PFDI-20) To assess the safety of the study pessary 	
Additional Objective(s) To assess proportion of subjects who are successfully fit and car the study pessary To assess the subjects' ability to insert and remove the study pessars to compare subjects' discomfort experienced with insertion and of their current pessaries with study pessaries To globally assess satisfaction associated with use of the study pessaries		
Research Intervention(s)/ Investigational Agent(s)	Replacement of a subject's current pessary with a study pessary for use over a three-month time interval	
IND/IDE #	Device to be considered for an abbreviated IDE (non-significant risk device)	
Study Population	Current users of a Gellhorn or ring style pessary for management of Stage II or greater pelvic organ prolapse	
Sample Size	40, excluding withdrawals	
Study Duration for individual participants	4 months	
Study Specific Abbreviations/ Definitions	CRAIQ – Colorectal Anal Impact Questionnaire EMR – Electronic Medical Record FPMRS – Female Pelvic Medicine and Reconstructive Surgery FSF – Female Sexual Function IIQ – Incontinence Impact Questionnaire IUGA – International Urogynecological Association PFDI-20 – Pelvic Floor Distress Inventory-20 PFIQ-7 – Pelvic Floor Impact Questionnaire-7 PFMT – Pelvic Floor Muscle Training PISQ-IR – Pelvic Organ Prolapse/Urinary Incontinence Sexual Questionnaire, IUGA-Revised POP – Pelvic Organ Prolapse POP-Q – Pelvic Organ Prolapse Quantification POPIQ – Pelvic Organ Prolapse Impact Questionnaire UI – Urinary Incontinence VAS – Visual Analogue Scale	

	WCG IRB – Western Copernicus Group IRB
	WCG IKB – Western Copernicus Group IKB

[figure not shown]
2.0 Objectives

The purpose of this study is to obtain preliminary data on the effectiveness, safety, function, comfort, and patient satisfaction with a novel vaginal pessary design for the use in women who suffer from symptoms of pelvic organ prolapse (POP) and have already opted for non-surgical management. Recruited subjects will have Stage II POP or greater and will be current users of a Gellhorn or ring style pessary. Following enrollment, each subject will enter a 1-month wash out period in which they will continue using their current pessary so that baseline subjective and objective data can be collected. They will then be fit with a study pessary and enter a 3-month treatment phase. Comparative, subjective and objective data will be collected at the conclusion of the study.

3.0 Background

POP is a prevalent condition that can be observed in over 50% of women over the age of 50.1 POP results from a weakening of the pelvic floor connective tissue and muscles, allowing the uterus or vaginal walls to descend. Typical symptoms, which include bulge and pressure, urinary dysfunction, defecatory dysfunction, and sexual dysfunction, can result in physical discomfort, emotional distress, and disrupt activities of daily life. Using published data on weighted prevalence rates of specific pelvic floor disorders² in conjunction with US census data, it can be estimated that the number of US women with symptomatic prolapse in 2016 was 3.6 million. The lifetime risk for a woman to have surgery for pelvic organ prolapse is 12.6%, or 1:8.3 As the specialty of Female Pelvic Medicine and Reconstructive Surgery (FPMRS) matures and surgical outcomes are being followed with more scrutiny, it is becoming increasingly clear that surgical treatment options are less effective than once believed. The 3 most effective and commonly performed procedures for apical prolapse have estimated composite recurrence rates by 6 years of 43%, 49%, and 57%.⁴

The vaginal pessary is an effective treatment option for POP. A pessary is inserted in the vagina and acts as a shelf resting upon the pelvic floor muscles to support the descending organs. A pessary is not surgically implanted and can be removed and reinserted but is only effective while in situ. Often, pessaries are as effective as reconstructive surgery in improving the symptoms of prolapse. 77% of practicing urogynecologists recommend a vaginal pessary as the first line treatment option for their patients with POP.⁵ It is estimated that there are ~2.3 million women in the United States who use a pessary for POP, based on financial information from pessary makers and the above epidemiologic data on POP. The root cause failure of current pessaries in common use is their rigid and fixed design, which makes them difficult or impossible for patients to remove and insert independently. Consequently, medical practitioners in the United States see most pessary users at least 3-4 times per year to temporarily remove the pessary, clean it, examine the

vagina for epithelial erosions, and then reinsert the pessary.⁶ These steps are needed to avoid preventable complications associated with long term pessary use which have been reported as high as 56%⁷ and include vaginal erosion, bleeding, increased discharge, as well as discomfort and dysfunction in voiding and defecation.⁸ Furthermore, women who experience less severe forms of prolapse and who do not need the support of their pessary outside of strenuous physical activity often must wear their pessary when not necessary, which induces additional lifestyle impacts such as impairing a woman's ability to engage in sexual intercourse.

The two most commonly used pessaries on the market are the "ring with support" and the "Gellhorn" pessary. The Gellhorn pessary is clinically more effective to reduce the life impact of prolapse symptoms, 9 and once fit has longer continuation rates than the ring with support (10.5 years vs. 1.8 years). 10 Additionally, the Gellhorn successfully treated 71% of women at 3 months who failed treatment with the ring with support. 11 Yet most practitioners, particularly Ob/Gyn physicians who are not additionally specialized in FPMRS, preferentially prescribe the ring style pessaries because they are easier and more intuitive to use. The Reia Vaginal Pessary (study pessary) has been engineered to improve the comfort and ability of pessary removal and reinsertion by physicians and patients. The Reia Vaginal Pessary has a structural form similar to the Gellhorn, but is collapsible, and is hypothesized to be simpler and more comfortable to use than ring style pessaries. This hypothesis is preliminarily supported by data obtained in an early feasibility, in-office trial with 15 subjects (NCT04275089).

4.0 Study Endpoints

The primary and secondary endpoints of the study are described in the following table:

Type	Name	Time Frame	Brief Description
Primary		the end of washout	The Pelvic Floor Distress Inventory -20 (PFDI-20) is a validated instrument to assess the presence and bother of symptoms that pelvic floor disorders have on health-related quality of life in women. It is a 20-item questionnaire and the short form of the 46 question PFDI. There are three subscales: Urinary Distress Inventory 6 (UDI-6), Colorectal-Anal Distress Inventory 8 (CRADI-8), and the Pelvic Organ Prolapse Distress Inventory 6 (POPDI-6). The overall score range is 0-300. The higher the score, the greater the perceived impact that pelvic floor dysfunction has on a patient's life. The minimal important change in the

D	ΙΛ	DOCUMENT NUMBER	CP-002-01	r 03
K			PAGE	7 of 23

TITLE COLLAPSIBLE PESSARY FEASIBILITY TRIAL PROTOCOL

PAGE 7 OF 23

			PFDI-20 to demonstrate a clinical effect in women choosing conservative management of their prolapse (i.e. a pessary) is between 13.5 and 18.3 points.
Primary	Prevalence and severity of adverse events that subjects experience using the study pessary compared to those experienced with their current pessary	Throughout study [Week 0-16] Adverse events can occur with use of the current pessary or during the treatment phase with the study pessary. They can be experienced with insertion or removal of either the current or study pessary, noted on physical exam, or reported at any time.	Adverse events experienced with insertion or removal of the current or study pessary include: pelvic cramping or discomfort, perineal tear, failure of the study pessary to deploy or collapse, or pessary expulsion. Adverse events noted on physical exam include: vaginal irritation, vaginal ecchymosis, vaginal abrasions/superficial cuts, vaginal erosion, vaginal bleeding, vaginal discharge, or urinary retention. Adverse events which could occur at any time include: pelvic cramping or mild discomfort, copious vaginal discharge, urinary tract infection, substantial discomfort, pessary expulsion (collapsed or deployed), or adverse events unrelated to the pessary or study visit. Each event will be classified as mild (transient and easily tolerated by the subject), moderate (causing discomfort or interrupting usual activities), or severe (causing considerable interference with usual activities, may be incapacitating, or may require hospitalization).
	Pelvic Floor Impact Questionnaire (PFIQ- 7)	Between enrollment and the end of washout	Pelvic Floor Impact Questionnaire -7 is a health-related quality of life instrument, designed to assess the life impact of pelvic floor symptoms in women with pelvic floor disorders. The PFIQ-7 has a parallel structure to the PFDI with 3 Scales: CRAIQ, POPIQ and IIQ.
Secondary	Pelvic Organ Prolapse/Urinary Incontinence Sexual	the end of washout	A validated evaluation tool which can be used clinically as well as in research for assessment of female

DEIA	DOCUMENT NUMBER	CP-002-01	r 03
KEIA		PAGE	8 of 23

TITLE COLLAPSIBLE PESSARY FEASIBILITY TRIAL PROTOCOL

	Questionnaire, IUGA- Revised (PISQ-IR)	[Week 0-4] and post treatment [Week 16]	sexual function (FSF) in women with female pelvic floor disorders.
	Objective assessment of the pessary's ability to support the prolapse	At enrollment [Week 0], during treatment [Week 3-5], and during treatment [Week 16]	POP-Q points Ba and Bp (measurements of prolapse) will be measured during physical exam, with the pessary in situ.
Secondary	Global assessment of study pessary satisfaction compared to current pessary	For current pessary at the end of washout period [Week 3-5]; For study pessary post treatment [Week 16]	Satisfaction will be assessed using a Visual Analog Scale (VAS) with a 10 cm linear continuum in which 0 represents no satisfaction and 10 represents complete satisfaction.
Secondary	Pain associated with study pessary insertion compared to current pessary	During treatment [Week 3-5], during treatment [Week 5-7], and post treatment [Week 16]	Pain will be assessed using a Visual Analog Scale (VAS) with a 10cm linear continuum in which 0 represents no pain and 10 represents worst pain.
	Pain associated with study pessary removal compared to current pessary	During treatment [Week 3-5], during treatment [Week 5-7], and post treatment [Week 16]	Pain will be assessed using a Visual Analog Scale (VAS) with a 10cm linear continuum in which 0 represents no pain and 10 represents worst pain.
Other	Proportion of subjects successfully fit with the study pessary	Post treatment [Week 16]	Proportion of subjects who were successfully fit with the study pessary.
Other	Change in frequency of pessary removal for self-managers	Post treatment [Week 16]	The monthly frequency of pessary self-removal during the washout period will be compared against monthly frequency of self-removal in the treatment phase.
Other	Ease of insertion of study pessary by subject for self-managers	Post treatment [Week 16]	Ease will be assessed using a Visual Analog Scale (VAS) with a 10cm linear continuum in which 0 represents most difficulty and 10 represents most ease.
Other	Ease of removal of study pessary by subject for self-managers	Post treatment [Week 16]	Ease will be assessed using a Visual Analog Scale (VAS) with a 10cm linear continuum in which 0 represents most difficulty and 10 represents most ease.

5.0 Study Intervention/Investigational Agent Please see attached document for device description and non-significant risk rationale.

THE COLLAPSIDEL PESSANTI LASIDILITI TRIAL PROTOCO

6.0 Procedures Involved

Methods

This is a non-randomized prospective trial. Treatment intervention will be non-blinded to the subject and the investigator. Subjects will serve as their own controls and enter the treatment phase of the study after a 1-month washout period of using their current pessary. Subjects will be recruited for this study from panels of patients in clinical practices specializing in Female Pelvic Medicine and Reconstructive Surgery (FPMRS). Inclusion will be based on pre-defined criteria outlined in "10.0 Inclusion and Exclusion Criteria."

The primary outcome measure will be the change in the scores of the Pelvic Floor Distress Inventory-20 (PFDI-20), administered first during the washout period while still using their current pessary and then at the conclusion of the treatment phase with the study pessary. The PFDI-20 is a validated health-related quality of life instrument to assess the *presence and bother of symptoms* in women with pelvic floor dysfunction. For women with relatively mild pelvic floor symptoms, a minimal important change (MIC) of between 13.5 and 18.3 points in the PFDI-20 score can be considered clinically relevant. At least fifty subjects will be enrolled, expecting that after drop-out and attrition at least 40 subjects will have completed the study. This provides power of .80 for a MIC equivalence limit of 17 points on the PFDI-20 scale.

There will not be discrimination based on race or ethnicity. It is anticipated that most participants will be post-menopausal as this reflects the demographic of women who suffer from this disorder.

The study will take place over 4 visits (Visit 0, Visit 1, Visit 2, and Visit 3).

Visit 0 [research purposes] will involve screening, enrollment, consent, subject questionnaires, and chart abstraction for historical data and will take place during a regularly scheduled pessary maintenance visit. The current pessary size and type will be recorded, and it will be observed in situ for the presence of rotation and its ability to support prolapse by measuring the distance of the most dependent compartment of the subject's prolapse to the hymen (POP-Q points Ba and Bp), as well as the distance from the leading edge of the current pessary, if a Gellhorn, to the hymen. After removal of the current pessary, a baseline physical exam will be conducted to assess for pre-existing vaginal pathology (ecchymoses, abrasions, superficial cuts, erosions, granulation tissue, bleeding) or urinary retention associated with current pessary use. Other exam elements will include assessment of vulvovaginal atrophy, pelvic muscle strength, perineal descent, and POP-Q points GH (with strain) and TVL. After cleaning, the current pessary will be replaced, and each subject will begin the washout period where they continue use of their current pessary. Either at this first visit or during the washout period, each subject will complete the PFDI-20, PFIQ-7, and PISQ-R to establish baseline scores. Self-

managers will track the frequency of removals. If the current pessary cannot be reinserted, they will be treated according to standard of care.

Visit 1 [research purposes] will aim to be scheduled between 3 and 5 weeks from Visit 0 (the conclusion of the washout period). Demographic and historical data will be extracted from the Electronic Medical Record (EMR) if not completed at Visit 0 and supplemented by the subject as needed. Global subject satisfaction of the current pessary will be assessed using a Visual Analog Scale (VAS) with a 10 cm linear continuum in which 0 represents no satisfaction and 10 represents complete satisfaction. As in Visit 0, the current pessary will be observed in situ for the presence of rotation and its ability to support prolapse by measuring the distance of the most dependent compartment of the subject's prolapse to the hymen (points Ba and Bp), as well as the distance from the leading edge of the current pessary to the hymen. The current pessary will be removed, washed, placed in a sealed bag, labeled and either stored or given to the subject for them to return with at their final visit. The physical exam will be repeated as in Visit 0, and the presence of perineal disruption associated current pessary removal will be noted. The appropriate study pessary size for the subject based on the provided mapping from the subject's current pessary and practitioner's expertise will be selected at random from the inventory of study pessaries, removed from its sealed bag, and the study pessary's serial number (labeled on the bag) will be recorded. The subject will be fit with the study pessary. If a study pessary cannot be fit, and the patient is willing, they can be fit with a different sized pessary at Visit 1 or can remain in the study and return for a second attempt to be fit with a study pessary at Visit 2. A VAS will be used to assess the perceived discomfort with removal of the current pessary and, separately, with insertion of the study pessary. For self-managers, ease of current pessary removal and reinsertion will be noted using a VAS and teaching will be provided on the proper technique to insert and remove the study pessary.

Visit 2 [research purposes] has the option to be omitted, at the discretion of the practitioner and the subject, and will be aimed to be scheduled within 1-3 weeks of Visit 1. The subject will receive a phone call just prior to this visit. The subject will be asked about pessary use and adverse events. If the subject is doing well without any study related concerns, the practitioner and subject can decide if this visit can be omitted. The purpose of this visit is to minimize unforeseeable risks associated with use of the study pessary and/or to refit a subject with a study pessary if the original one was expelled or could not be inserted during Visit 1. If conducted in person, physical exam will be performed to assess for vaginal pathology (ecchymoses, abrasions, superficial cuts, erosions, granulation tissue or bleeding) or urinary retention related to the study pessary, and all adverse events will be recorded. The study pessary will be observed in situ for the presence of rotation and its ability to support prolapse by measuring the distance of the most dependent compartment of the subject's prolapse to the hymen, as well as the distance from the leading edge of the study pessary to the hymen. Those subjects who

were not successfully fit with a study pessary in their first visit would be fit with a new study pessary.

Visit 3 [research purposes] will occur at the conclusion of the 3-month (from Visit 1) treatment phase - a typical length of time between routine visits for patients who choose long term pessary management of their prolapse. It can be scheduled in a window between 11 and 13 weeks from Visit 1. When the subject returns for Visit 3, a physical exam will be repeated, as in previous visits, for comparative data. The study pessary will be observed in situ for the presence of rotation and its ability to support prolapse by measuring the distance of the most dependent compartment of the subject's prolapse to the hymen (Points Ba and Bp), as well as the distance from the leading edge of the study pessary to the hymen. A VAS will be used to assess discomfort with removal of the study pessary, discomfort with reinsertion of their current pessary, and their global satisfaction of the study pessary. The subject will have been instructed to return with their current pessary which was removed in Visit 1. If the subject's current pessary is not brought to the visit, they will be given a new pessary of the size and style of their current pessary. Each subject will complete the PFDI-20, PFIQ-7, and PISQ-R for a post treatment comparison. For self-managers, other data collected will include frequency of removal and a VAS for ease of study pessary insertion and removal.

Additional Visits: Subjects will be seen as necessary and adverse events will be managed according to standard of care. If the study pessary falls out after Visit 1, the subject may be seen at their convenience for reinsertion or resizing. If a study pessary cannot be fit and retained, the subject will be withdrawn from the study and their current pessary will be placed. If the subject's current pessary is not brought to the visit, they will be given a new pessary of the size and style of their current pessary.

Special Circumstances: If a subject dies between Visit 1 and Visit 3, an attempt will be made to contact the coroner to retrieve the study pessary. If the study pessary cannot be retrieved, a copy of the death certificate will be obtained.

The study pessary is the only device that will be used in this trial. There will be no placebo devices placed. The study pessary is not cleared by the FDA, and a rationale is provided for a non-significant risk device claim in the attached documents.

Data Collected

See attached data collection forms. The data collected will be obtained through chart abstraction, verbal history, questionnaire responses, visual analogue scale response, and physical exam.

Data collected on adverse events will be described in "18.0 Provisions to Monitor the Data to Ensure the Safety of Subjects."

DEIA	DOCUMENT NUMBER	CP-002-01	r 03	
REIA		PAGI	E 12 OF 23	
TITLE COLLAPSIBLE PESSARY FEASIBILITY TRIAL PROTOCOL				

Forms will be filled out electronically or in ink and stored according to procedures outlined in "17.0 Data Management and Confidentiality."

Transition from Research Participation

At the conclusion of the study, each subject will have their current pessary replaced in their vagina, and they will be instructed to present for their next routinely scheduled follow up visit per their typical care. If a subject lost their original pessary or if they do not bring it to the final visit, they will be supplied with a new pessary identical to their original at no additional cost.

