13.0 Withdrawal of Subjects

Reasons for a subject to be withdrawn from the research study include:

- The subject is found to have a condition that does not allow participation in the research, such as a finding upon physical examination that excludes them from the study.
- The subject no longer tolerates their current pessary during the washout period or needs a different size or type of pessary during the washout period.
- The subject is not able to be fit with a study pessary at the conclusion of Visit 2, or the study pessary is repeatedly expelled.
- The study pessary causes discomfort or adverse reaction for which continued use is contraindicated.
- The subject has a reaction that requires immediate removal of the study pessary.
- The subject may withdraw themselves at any point for unforeseen circumstances.

DELA	DOCUMENT NUMBER	CP-002-01	r 03	
REIA		PAGE 16 OF 23		
TITLE COLLAPSIBLE PESSARY FEASIBILITY TRIAL PROTOCOL				

If a subject is removed from the study, already collected data may not be removed from the study database and will be handled with the same protocol as research data. The subject will receive the usual ongoing care for their pessary.

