14.0 Risks to Subjects

This study will involve greater than minimal risk. The subject could experience:

- Discomfort during insertion, use, or removal of the study pessary.
- Minor abrasion of the vagina or perineum with insertion or removal of the study pessary.
- Vaginal bleeding caused by the study pessary.
- Increased vaginal discharge caused by the study pessary.
- Vaginal epithelial erosion (superficial or deep) from using the study pessary.
- Difficulty urinating or leakage of urine caused by the study pessary.
- Difficulty with defecation caused by the study pessary.
- Embarrassment if the study pessary falls out.
- Minor discomfort if the study pessary rotates out of position or if it falls out.
- Inconvenience caused by the inability of the study pessary to support the subject's prolapse.

[figure not shown]
Each of the risks cited above exist for any patient who chooses a pessary for management of their prolapse and are not unique to the study pessary. Though inconvenient, these are not life threatening.

The novelty of our pessary lies in its ability to flex, which we hypothesize will make insertion and removal more comfortable for the subject. Because it does not contain buttons, mechanism, or moving parts, it does not have mechanical features subject to failure. The soft and pliable nature of the molded silicone should not be capable of pinching the vaginal epithelium when the study pessary is elongated for removal, but this metric will be followed.

In common clinical practice, patients often use their pessaries continuously for 3-6 months without removal or medical evaluation. Per our protocol, the Reia pessary is intended to be used for 3 months continuously, and each subject will be evaluated 1-3 weeks after the study pessary is initially placed to assess for the presence of adverse events. Each subject will be a current pessary user, and during the course of the trial they will be monitored more closely than had they continued to use their existing pessary.

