17.0 Provisions to Monitor the Data to Ensure the Safety of Subjects

Data Analysis and Data Monitoring

This is a non-randomized, non-blinded, feasibility study involving a vaginal pessary. Given that the intervention is known to be safe and well-tolerated and the total exposure to our pessary for each subject was chosen to be similar to the typical interval of continuous pessary use which is common in clinical practice for current pessary users, we don't believe a formal data safety monitoring committee is required. However, a data and safety monitoring plan will be in place. The data safety monitoring plan will focus on low intensity monitoring by the Data Safety Monitoring Team, comprised of the one clinician from each participating site and a biostatistician. The Data Safety Monitoring Team will meet monthly, or sooner if necessary. Their charge will be to review subject accrual,

adherence to study protocol, and monitor adverse events. Additionally, they will ensure prompt reporting of serious adverse events to WCG IRB and the study sponsor (Reia, LLC).

At each contact with the subject, the clinical investigator will seek information on adverse events by specific questioning and by examination. Information on all adverse events will be recorded for review by the Data Safety Monitoring Team. Moderate adverse events which represent a change in baseline from those experienced in the washout period will be reviewed by the Data Safety Monitoring Team within one week. Serious adverse events, as defined by FDA criteria, will be reviewed by the Data Safety Monitoring Team within 24 hours and reported to WCG IRB and the study sponsor (Reia, LLC). Careful monitoring of the recruitment, enrollment, study procedures, and adverse events will help protect the safety of the subjects and quality of the data.

[figure not shown]
Any unanticipated adverse device effects that are possibly, probably, or definitely related to the study intervention will be immediately evaluated by the sponsor, Reia, LLC. If it is determined that the adverse device effect presents an unreasonable risk to the subjects, the investigation will be terminated within 5 working days of making the determination and not more than 15 working days of first receiving notice.

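### A woman first fitted at Visit 2 has no scheduled check for 8-12 weeks, although Section 14.0 says every subject is evaluated 1-3 weeks after placement

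*Protocol*

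**What the plan says.** Section 6.0 sets out four visits. A woman who cannot be fitted at Visit 1 may be tried with another size there and then, or she "can remain in the study and return for a second attempt to be fit with a study pessary at Visit 2". The Visit 2 paragraph repeats this: those who "were not successfully fit with a study pessary in their first visit would be fit with a new study pessary". Section 13.0 agrees, since its withdrawal criterion for failure to fit reads "The subject is not able to be fit with a study pessary at the conclusion of Visit 2". A first placement at Visit 2 is thus a planned route through the study.

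The timing rules in Section 6.0 are:

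- Visit 2 "will be aimed to be scheduled within 1-3 weeks of Visit 1".
- A call precedes Visit 2: "The subject will receive a phone call just prior to this visit". If all is well, the practitioner and the woman may agree to skip the in-person visit.
- Visit 3: "It can be scheduled in a window between 11 and 13 weeks from Visit 1". Nothing moves this window when placement is later than Visit 1.

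Section 14.0 states, without exception, that "each subject will be evaluated 1-3 weeks after the study pessary is initially placed", and gives the detection of adverse events as the reason. Section 17.0 links active enquiry to contacts: "At each contact with the subject, the clinical investigator will seek information on adverse events by specific questioning and by examination".

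**The concern.** The early check in Section 14.0 counts from placement, whereas the visits in Section 6.0 count from Visit 1. The two agree for a woman fitted at Visit 1. They separate for a woman first fitted at Visit 2, because the visit meant to be her early check becomes the placement itself, and nothing replaces it.

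Section 6.0 gives one aim of Visit 2 as limiting unexpected risks from a device that the FDA has not cleared. For this woman the visit cannot serve that aim. Adverse events are also a primary endpoint. Active questioning depends on contact, so an event that arises and settles within the gap is recorded only if she contacts the clinic or recalls it at Visit 3. The statement in Section 14.0 is part of the protocol's description of risk and should be true of every subject.

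**Working it through.** **Inputs**

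| Item | Value | Source |
|---|---|---|
| Visit 0 to Visit 1 | 3-5 weeks (nominal 4) | Protocol 6.0, Visit 1 |
| Visit 1 to Visit 2 | 1-3 weeks (nominal 2) | Protocol 6.0, Visit 2 |
| Visit 1 to Visit 3 | 11-13 weeks (nominal 12) | Protocol 6.0, Visit 3 |
| Early check after placement | 1-3 weeks | Protocol 14.0 |

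**Step 1. Reproduce the plan's own figure.** Visit 3 from Visit 0 is 3 + 11 = 14 to 5 + 13 = 18 weeks, nominally 4 + 12 = 16. This matches the Week 16 label in the Section 4.0 endpoint table, so the windows are being read as intended.

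**Step 2. Gap from Visit 2 to Visit 3.**

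- Shortest (late Visit 2, early Visit 3): 11 - 3 = 8 weeks.
- Longest (early Visit 2, late Visit 3): 13 - 1 = 12 weeks.
- Nominal: 12 - 2 = 10 weeks.

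As a cross-check, the endpoint table's Week 5-7 and Week 16 labels give 16 - 7 = 9 to 16 - 5 = 11 weeks, inside the same range.

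**Step 3. Compare with Section 14.0.** Time past the 3-week limit is 8 - 3 = 5 to 12 - 3 = 9 weeks.

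**Step 4. Count scheduled contacts after the placement visit.** A woman fitted at Visit 1 has two: Visit 2 (as a call or in person) and Visit 3. A woman first fitted at Visit 2 has one, Visit 3. Her pre-visit call took place before placement.

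**Step 5. See whether an added check fits.** A call 1-3 weeks after Visit 2 falls 1 + 1 = 2 to 3 + 3 = 6 weeks after Visit 1. The shortest time left before Visit 3 is 8 - 3 = 5 weeks, so the Visit 3 window, Week 16 and the 4-month participation are unchanged.

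**The case against.** The strongest case against the point is that it matters little.

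- **The case is narrow.** The woman must fail every size tried at Visit 1, stay in the study, be fitted at Visit 2 and retain the device. The documents do not say how many women this would be. This stands, and it limits the weight of the point.
- **The interval is ordinary for pessary users.** Section 14.0 notes that continuous use for 3-6 months without medical review is common, and all participants have worn a pessary for more than 3 months. This lessens the worry. But it describes usual practice, and the protocol adds an early check for its own device despite that practice.
- **Help is available.** Section 6.0 provides unscheduled visits when needed and Section 17.0 a 24-hour contact number. Both reduce harm. Both also depend on the woman seeking help, whereas Section 14.0 says she will be evaluated.
- **The wording could be changed instead.** Qualifying the sentence in Section 14.0 would remove the contradiction. It would also leave these women without the check, when a phone call would supply it.
- **No excess risk is shown.** The documents do not say that women fitted at a second attempt have more adverse events. That is correct, and the point does not need it.
- **The sources are incomplete.** The Section 9.0 timetable is partly illegible in the text available for review, and the data collection form was not available. No legible text schedules a contact between Visit 2 and Visit 3.

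SAP 13.3.2 describes Visit 3 as 11-13 weeks after Visit 2. That clause explains a frequency analysis, and SAP 15.1 leaves data collection to the protocol. Read literally, it would lengthen the gap to 11-13 weeks.

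**Conclusion.** The concern holds as a minor inconsistency between Sections 6.0 and 14.0. For a woman first fitted at Visit 2, the first scheduled check comes 8-12 weeks after placement against the stated 1-3 weeks.

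This assumes that Visits 2 and 3 take place within their windows. Visit 2 is only a target, so 8-12 weeks is the planned range and not a strict bound. It also assumes that no unavailable form or illegible timetable entry schedules a further contact. The point covers first placements at Visit 2 only, not women fitted at Visit 1 and later refitted. It does not affect the PFDI-20 analysis or either success criterion. What it affects is early safety follow-up, and the capture of adverse events, in what may be very few women.

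**What to change.** Add one sentence to Section 6.0: any woman who first receives the study pessary at Visit 2 is telephoned 1-3 weeks after that placement, is seen in person if there are concerns, and has any adverse events recorded. This is the standard the protocol already accepts for women fitted at Visit 1, whose Visit 2 may be replaced by a call. Visit 3 stays at 11-13 weeks from Visit 1.

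The cost is one extra call for each such woman, a protocol amendment with IRB review, a place to record the call, and a decision on whether it is paid (Section 12.0 pays for Visit 2 even by phone). SAP 7.2.3 already takes adverse events from additional calls, so the analysis does not change.
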